
 To evaluate the polymorphic and treatment-emergent amino acid substitutions in the PA, PB1, PB2, and NA genes and drug susceptibility in patients with evaluable virus 	
 Polymorphic and treatment-emergent amino acid substitutions in the PA, PB1, PB2, and NA genes Drug susceptibility in patients with evaluable virus
Safety Objective	Corresponding Endpoints

 To evaluate the safety of baloxavir marboxil plus a SOC NAI compared with matching placebo plus a SOC NAI in hospitalized patients with influenza 	
 Compare the incidence and severity of AEs and SAEs Incidence of AEs leading to discontinuation Proportion of patients with any post-treatment ALT and AST above baseline and $>3 \times \text{ULN}$, $>5 \times \text{ULN}$, $>10 \times \text{ULN}$
Pharmacokinetic Objective	Corresponding Endpoints

 To evaluate the single- and multiple-dose pharmacokinetics of baloxavir 	
 Plasma concentrations of baloxavir (active metabolite) at specified timepoints After each dose, concentration at predose and 24 hours postdose will be summarized Non-compartmental PK parameters such as AUC, C_{\max} and $t_{1/2}$ (only for patients undergoing sequential PK sampling)
Exploratory Palatability and Acceptability Objective	Corresponding Endpoint

 To describe the palatability and acceptability of the oral suspension in hospitalized patients with influenza 	
 Number and proportion of patients reporting each palatability and acceptability response at each timepoint

AE=adverse event; AUC=area under the concentration–time curve; C_{\max} =maximum plasma concentration; ICU=intensive care unit; NAI=neuraminidase inhibitor; NEWS2=National Early Warning Score 2; PK=pharmacokinetic; RT-PCR=reverse transcriptase polymerase chain reaction; SAE=serious adverse event; SOC=standard-of-care; $t_{1/2}$ =half-life; TTCI=time to clinical improvement; $t_{1/2}$ =half-life; ULN=upper limited normal.

^a Criteria for each parameter noted in Section 6.4.2.

^b Incidence of post-treatment influenza-related complications as defined in Section 6.4.3.

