4.1.2 Exclusion Criteria

Patients who meet any of the following criteria will be excluded from study entry:

- Patients who have received more than 48 hours of antiviral treatment for *the current influenza infection* prior to screening
- Patients who have received baloxavir marboxil for the current influenza infection
- Known contraindication to neuraminidase inhibitors
- Patients hospitalized for exclusively social reasons (e.g., lack of caregivers at home)

- Patients expected to die or be discharged within 48 hours, according to the investigator's judgement
- Patients weighing <40 kg
- Patients with known severe renal impairment (estimated glomerular filtration rate <30 mL/min/1.73 m²) or receiving continuous renal replacement therapy, hemodialysis, peritoneal dialysis
- Patients with any of the following laboratory abnormalities detected within 24 hours prior to or during screening (according to local laboratory reference ranges:
 - ALT or AST level > 5 times the upper limit of normal (ULN)
 - OR
 - ALT or AST > 3 times the ULN and total bilirubin level > 2 times the ULN
- Pregnant or breastfeeding, or positive pregnancy test in a predose examination, or intending to become pregnant during the study or within 28 days after the last dose of study treatment
- Exposure to an investigational drug within 5 half-lives or 30 days (whichever is longer) of randomization
- Any serious medical condition or abnormality in clinical laboratory tests that, in the investigator's judgment, precludes the patient's safe participation in and completion of the study
- *Known hypersensitivity to baloxavir marboxil or the drug product excipients*

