4.5.7 Laboratory and Other Biological Samples

Samples for the following laboratory tests will be sent to local laboratories for analysis:

- Hematology: WBC count, RBC count, hemoglobin, hematocrit, platelet count, differential count (neutrophils, eosinophils, basophils, monocytes, lymphocytes, other cells)
- Chemistry panel (serum or plasma): sodium, potassium, chloride, bicarbonate, glucose, BUN or urea, creatinine, total protein, albumin, phosphorus, calcium, total bilirubin, ALP, ALT, and/or AST, uric acid, LDH
- Liver chemistry panel: total bilirubin, ALP, ALT and/or AST

- Pregnancy test
 - All women of childbearing potential will have a pregnancy test at screening (*urine or serum*). For those countries under VHP (*i.e., Belgium, Czech Republic, Estonia, Finland, France, Germany, Hungary, Romania, Spain, and Sweden*), as well as Netherlands, a serum pregnancy test is mandated at screening. Urine pregnancy tests will be performed at specified subsequent visits. If a urine pregnancy test is positive, it must be confirmed by a serum pregnancy test.

The following samples will be sent to the Sponsor or a designee for analysis:

- Plasma samples for PK analysis (see [Appendix 2](#))
- Serum antibody titers for influenza A and B viruses
- Nasopharyngeal swabs for influenza virology tests (*i.e., RT-PCR, 50% tissue culture infectious dose [TCID₅₀], phenotyping and genotyping according to the resistance analysis plan, drug susceptibility testing*) and non-influenza respiratory *bacterial and virus* coinfections panel (only at the screening visit)

Blood and urine sample collection may be performed by an MN professional. For sampling procedures, storage conditions, and shipment instructions, see the laboratory manual.

These samples will be destroyed when the final Clinical Study Report has been completed, with the following exception:

- Plasma samples collected for PK analysis may be needed for additional PK assay development and validation; therefore, these samples will be destroyed no later than 5 years after the final Clinical Study Report has been completed.

When a patient withdraws from the study, samples collected prior to the date of withdrawal may still be analyzed, unless the patient specifically requests that the samples be destroyed or local laws require destruction of the samples. However, if samples have been tested prior to withdrawal, results from those tests will remain as part of the overall research data.

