4.5.8 Liver Function Monitoring

Patients should be assessed for liver function prior to each dose of baloxavir marboxil or matching placebo.

On Day 1 and Day 4, the assessment is mandatory. On Day 1, the local laboratory full blood chemistry panel required as part of screening can be used for this assessment or prior blood results if tests conducted within 24 hours prior to screening. On Day 4, the

protocol-required local laboratory blood liver chemistry panel should be used for this assessment.

On Day 7, the local laboratory blood liver chemistry panel and associated review of liver chemistry is only required if the patient will receive baloxavir marboxil or matching placebo on this study day.

Results must be reviewed by the investigator before dose administration. Dosing will occur only if the clinical assessment and local laboratory liver chemistry panel values are acceptable (see [Appendix 4](#)).

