5.2.3 Adverse Events of Special Interest (Immediately Reportable to the Sponsor)

Adverse events of special interest are required to be reported by the investigator to the Sponsor immediately (i.e., no more than 24 hours after learning of the event; see Section 5.4.2 for reporting instructions). Adverse events of special interest for this study are as follows:

- Cases of potential drug-induced liver injury that include an elevated ALT or AST in combination with either an elevated bilirubin or clinical jaundice, as defined by Hy's Law (see Section 5.3.5.6)
- Suspected transmission of an infectious agent by the study drug, as defined as follows:

Any organism, virus, or infectious particle (e.g., prion protein transmitting transmissible spongiform encephalopathy), pathogenic or non-pathogenic, is considered an infectious agent. A transmission of an infectious agent may be suspected from clinical symptoms or laboratory findings that indicate an infection in a patient exposed to a medicinal product. This term applies only when a contamination of the study drug is suspected.

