- AST or ALT $> 3 \times$ ULN with signs or symptoms compatible with hepatitis or hypersensitivity (e.g., fatigue, nausea, vomiting, right upper quadrant pain or tenderness, jaundice, fever, rash, eosinophilia [$> 5\%$])

Action to be Taken by Investigator

If any abnormal liver chemistry criterion is met, the investigator or subinvestigator must do the following:

- Patients must be instructed to discontinue study medication immediately.
- Following the initial observed elevation, every effort should be made to have the patient return to the clinic within 72 hours (if already discharged from hospital) to repeat liver function chemistries and for further hepatic evaluation.
- Every effort should be made to have the patients monitored 2 to 3 times per week until liver function chemistries (i.e., ALT, AST, ALP, TBL) resolve, stabilize *per investigator judgement*, or return to within the normal range or to baseline levels.
- Consultation with a specialist, such as a hepatologist, and liver imaging (i.e., ultrasound, magnetic resonance imaging [MRI], computerized tomography) should be considered for worsening laboratory values or symptoms.

Appendix 5
Palatability and Acceptability Assessment of Study Drug

Questionnaire A: Adolescent (Age 12 to 15 Years) Palatability and Acceptability Assessment of Study Treatment Suspension (Baloxavir Marboxil or Placebo)

[figure not shown]
STUDY CP40617

Site Number: Visit Number:
Patient Number: Date:
Date Month Year

Instructions:

- Questionnaire A is to be utilized for adolescents aged 12–15 years unless they are considered to have a sufficient level of understanding to complete Questionnaire version B (Adolescents 16 years and above and adults).
- The questions below are to be completed approximately 1 minute after swallowing the drug solution and before rinsing the mouth.
- For Question 1, patients are encouraged to select, from the 5-point visual hedonic scale below, the face that best reflects how much he or she liked the taste of the ingested study drug solution.
- This questionnaire can be given to the patient to complete or the form can be completed by study personnel. The patient must provide answers to the questions.

1. How was the taste of the medicine?

2. Would you be happy to take the medicine again?

- yes
- no
- not sure/no answer

Appendix 5
Palatability and Acceptability Assessment of Study Drug (cont.)

**Questionnaire B: Adult and Adolescent (Age 16 Years and Above) Palatability

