4.7.3 Laboratory Data

All laboratory data will be converted to SI units. The International Standard for the Handling and Reporting of Laboratory Data COG 3007 (Version 4.0) will be used to implement reference ranges and marked abnormalities for laboratory data where possible.

For each of the haematological and biochemical test parameters, summary statistics of observed and change from baseline values at Day 10 will be presented by treatment group. Baseline is defined as the last assessment prior to treatment on Day 1.

A listing will present all lab assessments data for patients who had any significant change from baseline.

Summaries of the number of patients by CTC grade at each assessment will also be presented. For laboratory parameters, observations on Day 1 will be classed as baseline.

Additionally, summary statistics of observed and change from baseline values of liver function tests (Total Bilirubin, Alkaline phosphatase [ALP], Alanine aminotransferase [ALT] and aspartate aminotransferase [AST]), which are collected on Day 1, Day 4, Day 7 (if 3rd dose of baloxavir received) and Day 10, will be presented by treatment group for each scheduled time point, as well as box and whisker plots at each time point.

The number and proportion of patients who meet the pre-specified criteria shown in [Table 14](#) will be presented by treatment group during the study.

Table 14 Pre-specified Abnormal Laboratory Criteria

AST (U/L) or ALT (U/L) and Total bilirubin (mg/dL)
AST(U/L) or ALT (U/L) > 3 × ULN
AST(U/L) or ALT (U/L) > 5 × ULN
AST (U/L) or ALT (U/L) > 3 × ULN and Total bilirubin (mg/dL) > 2 × ULN

ALT= Alanine aminotransferase; AST= aspartate aminotransferase; ULN = upper limit of normal.

A listing of all pregnancies will be presented.

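### One transaminase satisfies the laboratory panels in Protocol 4.5.7, but the liver safety endpoint and SAP 4.7.3 rely on both ALT and AST

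*Protocol*

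**What the plan says.** Protocol 4.5.7 lists two panels run at local laboratories. The full chemistry panel (screening and Day 10) includes "total bilirubin, ALP, ALT, and/or AST, uric acid, LDH". The liver panel (Day 4, and Day 7 if a dose is planned) is "Liver chemistry panel: total bilirubin, ALP, ALT and/or AST". Both leave the site free to report one transaminase. Nothing requires the same one at each visit.

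Other parts of the plan use the two enzymes in two ways.

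- **Both enzymes.** The safety endpoint (Table 1 of the Protocol and of the SAP) begins "Proportion of patients with any post-treatment ALT and AST above baseline and" and continues with the multiples 3, 5 and 10 × ULN. SAP 4.7.3 plans observed values and change from baseline for "liver function tests (Total Bilirubin, Alkaline phosphatase [ALP], Alanine aminotransferase [ALT] and aspartate aminotransferase [AST", and describes these tests as collected on Days 1, 4, 7 (with a third dose) and 10. Protocol Appendix 4 asks for repeat monitoring "until liver function chemistries (i.e., ALT, AST, ALP, TBL) resolve" or otherwise settle, but only once a criterion has been met.
- **Either enzyme.** The exclusion criterion reads "ALT or AST level > 5 times the upper limit of normal (ULN", with a second limb that adds bilirubin. The adverse event of special interest (Protocol 5.2.3), the Hy's Law reporting rule (5.3.5.6), the Appendix 4 criteria and SAP Table 14 are also written with *or*.

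The same panel supports the pre-dose check in Protocol 4.5.8: "Dosing will occur only if the clinical assessment and local laboratory liver chemistry panel values are acceptable". SAP 4.10 has no rule for an enzyme that was not measured.

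**The concern.** The collection rule is looser than the analysis that depends on it. A site can follow 4.5.7 fully and still not supply the data that the endpoint and SAP 4.7.3 assume. With local laboratories at about 250 sites, what is measured depends on local practice.

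Liver injury is one of two named adverse events of special interest, and the transaminase endpoint is one of three listed safety endpoints. Elevations confined to an unmeasured enzyme would be absent from the tables without any sign that they are missing. The same gap reduces the sensitivity of the eligibility and pre-dose checks in the patients concerned.

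**Working it through.** The plan gives no figure on this point to reproduce. The first two steps compare text. The rest is an illustration on assumed values.

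**1. Is there any other route to both enzymes?** No section requires both at a scheduled panel. Appendix 4 names both only after a threshold has been crossed, so it cannot recover an elevation in an enzyme that was never run. SAP 4.7.3 describes both as collected, but a SAP does not set what sites collect.

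**2. What one enzyme does to each use.**

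- *Endpoint read as each enzyme separately:* the unmeasured enzyme is missing.
- *Endpoint read as both elevated:* a measured value that is not elevated settles a non-case; a measured value that is elevated leaves the patient undetermined.
- *Change from baseline:* not computable if the enzyme differs between baseline and the later visit.
- *Either-enzyme criteria:* still triggered by the measured enzyme, blind to the other.

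**3. Loss within one-enzyme patients.** Assumptions, not in the documents: each enzyme exceeds 3 × ULN with probability p, and the log values are bivariate normal with correlation ρ. Then P(either) = 2p − P(both), and the share of either-enzyme cases missed is 1 − p / P(either).

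| p | ρ | P(both) | P(either) | Missed |
|---|---|---|---|---|
| 5% | 0.7 | 1.96% | 8.04% | 38% |
| 5% | 0.8 | 2.48% | 7.52% | 34% |
| 5% | 0.9 | 3.19% | 6.81% | 27% |

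For example, at ρ = 0.7: 2 × 5% − 1.96% = 8.04%, and 1 − 5/8.04 = 0.378. With p = 10% the loss is 24–35%; with p = 3% it is 28–40%.

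**4. Loss over the whole trial.** If a share f of patients has one enzyme, the overall loss is f times the figure above. Using the unrounded 26.6% to 37.8% at p = 5%:

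- f = 0: none.
- f = 5%: 0.05 × 26.6% = 1.3% to 0.05 × 37.8% = 1.9%.
- f = 25%: 0.25 × 26.6% = 6.7% to 0.25 × 37.8% = 9.5%.

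In patients, if all 366 are treated, the expected number lost is f × (P(either) − p) × 366. At f = 25% that is 0.25 × 1.81% × 366 = 1.7 to 0.25 × 3.04% × 366 = 2.8, out of about 25 to 29 true cases (6.81% and 8.04% of 366).

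**5. Direction of error.** For either-enzyme criteria, one enzyme can only undercount. If the endpoint means both elevated, scoring it on one enzyme would overcount: 5% against a true 2.0–3.2%, a factor of 5/3.19 = 1.6 to 5/1.96 = 2.6.

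**6. SAP Table 14 against the endpoint.** Table 14 uses *or*, at > 3 and > 5 × ULN, plus > 3 × ULN with bilirubin > 2 × ULN. It has no > 10 × ULN row and no above-baseline condition. Requiring both enzymes would not by itself make Table 14 deliver the endpoint in Table 1.

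**The case against.** The strongest reply is that 4.5.7 also permits both enzymes, many laboratories may run both, and the SAP's statement that both are collected may describe what happens. On that view 4.5.7 is only loosely worded. There are safeguards too: total bilirubin and ALP are in both panels, dosing also needs an acceptable clinical assessment, clinical jaundice counts towards the special-interest event, and clinically significant laboratory abnormalities are reportable. Safety is summarised descriptively in a randomised, blinded trial.

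Much of this stands, and it rules out several stronger readings.

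- A reader might infer that the endpoint cannot be evaluated at all. It can be wherever both enzymes are run, and Table 14 can be computed from one.
- A reader might infer that the plan treats an unmeasured enzyme as normal. Neither document says so; they are silent.
- A reader might infer that all liver rates are understated. That follows only for the either-enzyme criteria; under the both-elevated reading the error could go the other way.
- A reader might take 27–38% as the trial-wide loss. It applies only within one-enzyme patients.

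The reply does not remove the mismatch. The text allows one enzyme, the endpoint and SAP 4.7.3 need two, and the safeguards do not reveal an isolated rise in the enzyme that was not run.

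**Conclusion.** The point holds as a mismatch between data collection and analysis. Protocol 4.5.7 does not secure the data that the liver endpoint and SAP 4.7.3 rely on. In one-enzyme patients the endpoint is not fully evaluable, change from baseline may be missing, and either-enzyme criteria keep working with lower sensitivity.

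The size is unknown because the share of one-enzyme patients is not stated. The illustrative losses in the working also rest on an assumed elevation rate and correlation. Which enzymes are run depends on the local laboratory, not on the blinded allocation, so the arm comparison is not biased by site; it loses some events. This should be corrected, but it does not undermine the safety analysis as a whole.

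**What to change.** - **Protocol 4.5.7:** require ALT and AST in both the chemistry panel and the liver panel, so that collection matches the endpoint and SAP 4.7.3.
- **SAP Table 14:** align it with the Table 1 endpoint. State whether the criterion is *and* or *or*, add > 10 × ULN, and add the above-baseline condition.
- **SAP 4.7.3 denominators:** for each enzyme, use patients with that enzyme measured after baseline. Require a baseline value only for the above-baseline criterion and the change-from-baseline summaries; requiring it everywhere would drop patients with a post-dose elevation and no baseline for that enzyme. For the *or* criteria, show one-enzyme patients separately.
- **Eligibility and pre-dose check:** the panel definition in 4.5.7 must be reconciled with the liver thresholds in 4.1.2, 4.5.8 and Appendix 4. No threshold or dosing rule is proposed here.

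The cost is one further assay at local laboratories that now run one enzyme, normally on the sample already drawn. Protocol 4.5.8 lets Day 1 rely on a result from up to 24 hours before screening; where that result has one enzyme, a new sample may be needed. Some observed elevation rates on the *or* criteria may rise slightly.

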4.5.8 Liver Function Monitoring

Patients should be assessed for liver function prior to each dose of baloxavir marboxil or matching placebo.

On Day 1 and Day 4, the assessment is mandatory. On Day 1, the local laboratory full blood chemistry panel required as part of screening can be used for this assessment or prior blood results if tests conducted within 24 hours prior to screening. On Day 4, the

protocol-required local laboratory blood liver chemistry panel should be used for this assessment.

On Day 7, the local laboratory blood liver chemistry panel and associated review of liver chemistry is only required if the patient will receive baloxavir marboxil or matching placebo on this study day.

Results must be reviewed by the investigator before dose administration. Dosing will occur only if the clinical assessment and local laboratory liver chemistry panel values are acceptable (see [Appendix 4](#)).

4.5.9 Electrocardiograms

Single ECG recordings will be obtained at specified timepoints, as outlined in the schedule of activities (see [Appendix 1](#)) and may be obtained at unscheduled timepoints.

All ECG recordings must be performed using a standard high-quality, high-fidelity digital electrocardiograph machine equipped with computer-based interval measurements. Lead placement should be as consistent as possible. ECG recordings must be performed after the patient has been resting in a supine position for at least 10 minutes. All ECGs are to be obtained prior to other procedures scheduled at that same time (e.g., vital sign measurements, blood draws) and, if possible, should not be obtained within 3 hours after any meal. Circumstances that may induce changes in heart rate, including environmental distractions (e.g., television, radio, conversation) should be avoided during the pre-ECG resting period and during ECG recording.

For safety monitoring purposes, the investigator must review, sign, and date all ECG tracings. Paper copies of ECG tracings will be kept as part of the patient's permanent study file at the site.

4.5.10 Chest X-Rays/CT scan

If a chest X-ray has not been taken within the 24 hours prior to screening, it must be performed on Day 1. If a chest X-ray was performed within 24 hours prior to screening, no additional chest X-ray needs to be performed. If the SOC is a chest CT scan, this can be used as alternative to the chest X-ray.

Chest X-ray/CT scan findings should be recorded on the appropriate eCRF at baseline. If additional chest X-rays/CT scans are taken per local practice, this information should be provided in the CRF.

4.5.11 Rapid Influenza Diagnostic Test

For patients to be eligible for this study, a RIDT or RT-PCR is required to be performed to inform a diagnosis of influenza. A patient with a negative RIDT may be enrolled if influenza is suspected based on local surveillance data or the patient reports contact

with a known case of influenza within the prior 7 days and this is documented; the patient must meet all other inclusion criteria.

The RIDT will be provided by the Sponsor for sites that do not have access to a local RIDT kit or who do not perform RIDT as standard of care. If a site has performed a RIDT or RT-PCR test within the 24 hours prior to screening, the local RIDT or RT-PCR result can be used, and the test result will be entered into the eCRF.

